## 2 PROTOCOL SYNOPSIS & FLOW CHART

Title	An observational study of the Q Aspiration Catheter used during neurointervention for acute large vessel ischemic stroke in Spain.
Description	The TAPAS Study: Thrombectomy Aspiration Post market study in Acute Stroke
Sponsor	MIVI Neuroscience, Inc.
Protocol No.	101347 Rev B
Study Device	MIVI Q Aspiration Catheter (CE Marked)
Primary Efficacy Endpoint	Successful revascularization defined as final mTICI 2b-3 flow in the target vessel.
Primary Safety Endpoint	Symptomatic intracranial haemorrhage post- procedure as detected by CT scan/ MRI with an NIHSS change of $\geq 4$ .
Secondary Endpoints	

Successful revascularization defined as mTICI 2b-3 flow in the target vessel post-treatment with the Q Catheter alone (first line therapy)

Embolization to a new neurovascular territory

Good functional outcome of Modified Rankin Score of 0-2 at 90 days

Mortality at 90 days

Inclusion Criteria	

Age 18 to 85 years

Diagnosis of acute ischemic stroke with mechanical thrombectomy procedure <math>< 8</math> hours from onset of symptoms/ last well known well

Large Vessel Occlusion on CT scan or MRI in the Anterior Cerebral Vasculature up to A1, M1, M2, or Posterior Cerebral Vasculature

ASPECTS 6 – 10 or volume of diffusion restriction <math>< 50</math> mL

Use of the Q Aspiration Catheter as the first line treatment according to the IFU

Signed informed consent form

Exclusion Criteria	

Occlusions in multiple vascular territories, extracranial or tandem occlusion

Evidence of dissection in the carotid or target artery for treatment

Evidence of recent/fresh haemorrhage on presentation

Unwilling to agree to a 3 month follow up visit

Follow-up	Subject will have one visit at about 3 months post-procedure.
Scope	This study will enroll a total of 50 subjects at up to 5 investigational sites in Spain.

### 3 BACKGROUND

#### 3.1 Overview

Stroke is the second single most common cause of death in Europe accounting for almost 1.1 million deaths each year, based on data from WHO estimated the number of strokes in the year 2000. Furthermore, it has been predicted that stroke incidence will increase to 1.5 million per year by 2025, largely owing to the increasing proportion of elderly individuals.

Ischemic strokes represent approximately 87% of all strokes while the remaining 13% are hemorrhagic. The chief goal in treating acute ischemic stroke is to restore cerebral blood flow as rapidly and safely as possible. Currently there are two approaches to treatment, intravenous (IV) delivery of Tissue Plasminogen Activator (tPA), a thrombolytic agent, and mechanical thrombectomy. Combining IV tPA treatment with mechanical thrombectomy has recently been shown to demonstrate an advantage with good clinical results for patients.

Endovascular treatment using mechanical devices to recanalize the occluded vessel include the use of catheters to directly deliver a clot-disrupting or retrieval device to the thrombus, this includes aspiration catheters, stent-retrievers and other clot disrupting devices. However, withdrawing the clot disrupting devices by mechanical force to perform thrombectomy may increase the risk of vascular intimal injury and the incidence of vasospasm. Therefore, aspirating clot may be preferred to reduce vessel damage during recanalization. Mechanical revascularization using an aspiration catheter as the primary approach to clot removal is commonly performed and

[figure not shown]
sometimes referred to as the ADAPT technique. The ADAPT technique is favored by some physicians because of its potential to be less traumatic to the neurovasculature and improve on time to revascularization compared to stent retrievers.

The MIVI Neuroscience, Inc. CE Marked Q Aspiration Catheter is a family of short, extension catheters introduced through an 8F guide catheter/6F sheath. Aspiration is performed from the short Q Catheter into the guide catheter/sheath. The MIVI Neuroscience, Inc. Q Aspiration Catheter may offer an increased force of aspiration from the larger 8F guide lumen and the potential access to more distal clot with the small Q Catheter lumen.

### 3.2 Q Aspiration Catheter Description

The MIVI Q Aspiration Catheter consists of a single lumen, variable stiffness shaft with radiopaque markers are included on the distal and proximal end of the catheter portion for angiographic visualization. The catheter shaft has a hydrophilic coating to reduce friction during use. The proximal portion of the catheter is a stainless-steel control wire. The Q Aspiration Catheter is designed to be used with an 8F guide/6F sheath for use in the removal of fresh, soft emboli and thrombi in the neurovascular system.

**FIGURE 1 6F Q Catheter Illustration & Drawing**

**TABLE 1 Q Dimensions and Configurations**

Device	Total Length (cm)	Catheter Section Length (cm)	Proximal Catheter Section ID	Proximal Catheter Section OD	Distal Catheter Section ID	Distal Catheter Section OD
Q6 6F Catheter	145	25	1.75 mm (0.069")	2.24 mm (0.088") 6.7F	1.75 mm (0.069")	2.13 mm (0.084") 6.4F
Q5 5F Catheter	145	25	1.45 mm (0.057")	2.24 mm (0.088") 6.7F	1.45 mm (0.057")	1.83 mm (0.072") 5.5F
Q4 4F Catheter	150	30	1.45 mm (0.057")	2.24 mm (0.088") 6.7F	1.09 mm (0.043")	1.4 mm (0.055") 4.2F
Q3 3F Catheter	163	43	1.45 mm (0.057")	2.24 mm (0.088") 6.7F	0.91 mm (0.036")	1.22 mm (0.048") 3.7F

### 3.3 Intended Use

The Q Aspiration Catheter is indicated for use in the removal of fresh, soft emboli and thrombi in the peripheral and neurovascular systems. It may also be used as a diagnostic angiographic catheter.

It is intended to be used by physicians skilled in the field(s) Interventional Radiology, Interventional Neuroradiology, Neurosurgery and/or Neurology who are skilled in endovascular interventional procedures for acute ischemic stroke.

The Q Catheter is a family of short, extension catheters that is introduced through an 8F catheter. Aspiration is performed from the short Q and into the 8F catheter. The Q is visible under fluoroscopy and must be hydrated for at least 1 minute in saline prior to use. The Q is typically introduced over a guidewire and is advanced to the desired vessel in the neurovasculature under fluoroscopy. Once in place, tubing attached to a vacuum pump and to the stopcock of an 8F catheter. Thrombus is then aspirated through the Q and into the 8F catheter. At the end of the procedure, all devices are carefully removed and discarded. Device compatibility is in **Table 2** below.

**TABLE 2 Q Compatibility**

Device	Maximum Guidewire Size	Maximum Microcatheter Size	8F Guide Catheter / 6F Sheath ID Range
Q6 6F Catheter	0.035"	5.0F	0.088" – 0.090" (2.2 – 2.3 mm)
Q5 5F Catheter	0.035"	4.0F	0.088" – 0.090" (2.2 – 2.3 mm)
Q4 4F Catheter	0.035"	3.0F	0.088" – 0.090" (2.2 – 2.3 mm)
Q3 3F Catheter	0.018"	2.4F	0.088" – 0.090" (2.2 – 2.3 mm)

The MIVI Super 90 Guide Catheter or any other commercially available and compatible 8F catheter may be used with the Q Catheter.

The Q Aspiration Catheter is a Class III medical device in the EU and obtained CE Mark in March 2018.

## 4 STUDY DESIGN AND OBJECTIVES

### 4.1 Study Purpose and Design

The purpose of this study is to demonstrate the safety and performance of the MIVI Neuroscience, Inc. Q Aspiration Catheter for use in the removal of fresh, soft emboli and thrombi in the neurovascular system during acute ischemic stroke. The study is an observational study that will enroll a maximum of 50 subjects in Spain.

Subjects will be followed through hospitalization and a visit 3 months post-procedure. A maximum of 5 sites in Spain will be involved in this study. Enrollment is expected to take approximately 6 months.

### 4.2 Primary Endpoints

The primary performance endpoint is successful revascularization defined as final mTICI 2b-3 flow in the target vessel.

The primary safety endpoint is symptomatic intracranial haemorrhage at 24 hours post-procedure as detected by CT scan/MRI with an NIHSS change of greater than or equal to 4.

### 4.3 Secondary Endpoints

- Successful revascularization defined as mTICI 2b-3 flow in the target vessel post-treatment with the Q Catheter alone (first line therapy)
- Embolization to a new neurovascular territory
- Good functional outcome measured by Modified Rankin Score of 0-2 at 90 days
- Mortality at 90 days

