### **6.3 Inclusion Criteria**

Subjects who meet the following criteria may be included in the study:

1. Age 18 to 85 years;
2. Diagnosis of acute ischemic stroke with mechanical thrombectomy procedure < 8 hours from onset of symptoms or last known well;
3. Large Vessel Occlusion on CT scan or MRI in the Anterior Cerebral Vasculature up to A1, M1, M2, or Posterior Cerebral Vasculature;
4. ASPECTS 6 – 10 or volume of diffusion restriction < 50 mL;
5. Use of the Q Aspiration Catheter as the first line treatment according to the IFU;
6. Signed informed consent by patient or legally authorized representative.

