### **6.4 Exclusion Criteria**

Subjects who meet any one of these criteria will be excluded from the study:

1. Occlusions in multiple vascular territories (e.g., bilateral anterior circulation, or anterior/posterior circulation) extracranial occlusion or tandem occlusion;
2. Evidence of dissection in the carotid or target artery for treatment;
3. Evidence of recent/fresh haemorrhage on presentation;
4. Unwilling to agree to a 3-month follow up visit.

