## **8.2 Baseline**

Baseline data will only be collected after the subject has agreed to participate and signed an informed consent form. Baseline data collected will include: hospital transfer, age, sex, vital signs (height, weight, blood pressure, respirations, etc), pertinent medical history, pre-treatment NIHSS, pre-stroke Modified Rankin Score, neuroimaging results, and thrombolytic therapy.

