## **10.2 Statistical Methods**

This study is a single arm, registry study with endpoints compared to well defined and published outcomes. This study is designed for observational data to be collected and reported. There will be no formal statistical hypothesis testing conducted, and therefore sample size is not based on power calculations.

Data analysis will comprise of descriptive statistics (means, standard deviations, rates, correlations, etc.) on the variables detailed in the study endpoints and other data collected.

The analyzed population will consist of all subjects who signed an informed consent form.

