### **10.3 General Statistical Considerations**

All endpoints will be analyzed descriptively. In general, continuous parameters will be summarized by number of evaluable observations, mean, standard deviation, median, minimum, and maximum. Categorical data will be described by frequency counts and percentages.

Every effort will be made to collect complete data. Unless otherwise specified, imputation of missing data will not be performed. Given the timing for evaluation, missing data is expected to be minimal to none for the primary safety and effectiveness endpoints. The primary analysis for the primary endpoints will include all subjects in the analysis population.

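### The comparison of mRS 0-2 and 90-day mortality with published outcomes takes no account of pre-treatment NIHSS, so a difference may reflect severity mix and not the device

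*Combined protocol and SAP*

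**What the plan says.** The functional endpoint in Section 4.3 is "Good functional outcome measured by Modified Rankin Score of 0-2 at 90 days". Mortality at 90 days is listed with it, and Section 13.2 specifies all causes.

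Section 10.2 describes how results will be put in context: "This study is a single arm, registry study with endpoints compared to well defined and published outcomes". It names no series, rate or comparator population. The references in Section 15 are cited only in the background (Section 3.1) and are not designated as comparators. Section 10.2 also rules out formal hypothesis testing. It allows descriptive statistics, correlations among them, on the endpoints and on other data. For a categorical endpoint, Section 10.3 says "Categorical data will be described by frequency counts and percentages".

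Eligibility bounds several prognostic features but not NIHSS. Section 6.3 includes "Age 18 to 85 years", "Diagnosis of acute ischemic stroke with mechanical thrombectomy procedure < 8 hours from onset of symptoms or last known well", an occlusion site, and ASPECTS 6 to 10 or "volume of diffusion restriction < 50 mL". Section 6.4 excludes multiple, extracranial or tandem occlusion, dissection, "Evidence of recent/fresh haemorrhage on presentation", and refusal of follow-up. The synopsis and Sections 6.1 and 8.3 add no NIHSS limit.

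Baseline severity is recorded. Section 8.2 lists "pertinent medical history, pre-treatment NIHSS, pre-stroke Modified Rankin Score, neuroimaging results, and thrombolytic therapy", and Table 3 schedules NIHSS at baseline and at 0-36 hours.

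**The concern.** The study has no control arm, so a functional or mortality rate from at most 50 subjects gains meaning mainly from being set beside a published rate. That is informative only if the two groups had a similar outlook before treatment. The plan neither restricts severity at entry nor uses the recorded severity when these two outcomes are compared.

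If this cohort is milder than the published series, mRS 0-2 will look better and mortality lower even when the catheter performs identically. A more severe cohort reverses both. Section 4.1 gives the purpose as demonstrating safety and performance, and Section 5.3 says no clinical investigation data exist yet, so such differences are likely to be read as evidence about the device. Pre-stroke mRS has the same gap: it is collected, has no eligibility limit, and is not used in the comparison.

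**Working it through.** There is no plan figure to reproduce: 50 is a cap, and Section 10.2 says it does not rest on a power calculation.

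**Step 1. Where NIHSS is used.** The endpoint text in Section 4.2, the hospital assessment in Section 8.4 and the definition in Section 13.2 all use an NIHSS change of at least 4 points for symptomatic haemorrhage. Table 3 has only one NIHSS before the post-procedure one, so the pre-treatment value is the evident reference. No functional or mortality analysis in Sections 10.2, 10.3 or 13.2 mentions NIHSS.

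**Step 2. How far severity mix can move a crude rate.** The documents give no rates by severity and no case mix. Every stratum rate and share below is therefore an assumption, including the premise that outcome worsens with severity. Device effect is set to zero: stratum rates are the same in study and comparator.

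Crude rate = (mild share × mild rate) + (moderate share × moderate rate) + (severe share × severe rate).

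Assumed comparator mix, mild/moderate/severe: 20/50/30. Assumed milder study mix: 50/40/10. Assumed more severe study mix: 10/40/50.

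| Outcome and assumed rates, mild/moderate/severe | Comparator | Milder study | More severe study |
|---|---|---|---|
| mRS 0-2, 70/50/25% | 46.5% | 57.5% (+11.0) | 39.5% (-7.0) |
| mRS 0-2, 60/50/35% | 47.5% | 53.5% (+6.0) | 43.5% (-4.0) |
| Death, 6/14/28% | 16.6% | 11.4% (-5.2) | 20.2% (+3.6) |
| Death, 10/14/20% | 15.0% | 12.6% (-2.4) | 16.6% (+1.6) |

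First row: 0.20 × 70 + 0.50 × 50 + 0.30 × 25 = 46.5, against 0.50 × 70 + 0.40 × 50 + 0.10 × 25 = 57.5.

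In absolute size, mRS 0-2 shifts by 4.0 to 11.0 points and mortality by 1.6 to 5.2 points.

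**Step 3. A simpler two-group check.** Assume 45% reach mRS 0-2 in moderate or severe strokes and 70-80% in mild strokes, with a comparator that has no mild strokes. A 20% mild share gives 0.2 × 70 + 0.8 × 45 = 50.0% up to 0.2 × 80 + 0.8 × 45 = 52.0%, a shift of 5.0 to 7.0 points. A 30% share gives 52.5% to 55.5%, a shift of 7.5 to 10.5 points. The standard error at n = 50 is √(0.45 × 0.55 / 50) = 7.0 points.

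**Step 4. Sampling error for scale.** The exact (Clopper-Pearson) 95% interval is 35.5% to 64.5% for 25/50, a half-width of (64.5 - 35.5)/2 = 14.5 points. The normal approximation, 1.96 × √(0.5 × 0.5 / 50), gives 13.9. For 8/50 deaths the exact interval is 7.2% to 29.1%. The case-mix shift is smaller than the mRS half-width, but it is a bias that the interval does not show.

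**Step 5. What an expected count does.** Take the milder mix at n = 50: 25 mild, 20 moderate and 5 severe. With the first-row rates, the expected count is 25 × 0.70 + 20 × 0.50 + 5 × 0.25 = 28.75. The crude published rate would lead one to expect 50 × 0.465 = 23.25. The apparent excess of 5.5 good outcomes is severity mix alone, and it disappears when the expected count uses this study's NIHSS distribution.

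**The case against.** The strongest reply is that this is a descriptive post-market registry. These endpoints are secondary, the primary performance endpoint is angiographic, nothing is tested, and no device effect on mRS or death is claimed. The wording on correlations and other data would already allow an NIHSS table. Age, vessel and imaging-core limits narrow the case mix. The sizes above are assumed, and at a 20% mild share the shift does not exceed one standard error. The strata would be small: with about 50/3 ≈ 17 subjects per band, the half-width near 50% is about 1.96 × √(0.25/17) ≈ 24 points.

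Much of this stands, and it limits the weight of the point. It does not remove it. Section 10.2 still promises a comparison, and an untested comparison can be confounded just as a tested one can. Permission for an NIHSS table is not a specification, and bands chosen after outcomes are known are open to selection. The entry limits do not align this cohort with a published series' NIHSS range.

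A reader might also infer more than the documents support:

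- **That the missing NIHSS limit is itself a defect.** An observational study of standard-of-care use need not have one.
- **That NIHSS enters no endpoint at all.** It enters the primary safety endpoint through the change score.
- **That severity is the main confounder.** This is not shown. Pre-stroke mRS bears directly on mRS 0-2. For mortality, consent as late as the 3-month visit (Section 7.2, Table 3) and logging death as a screen-failure reason (Section 8.1) raise a separate selection problem.

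**Conclusion.** The point holds as a gap in the planned comparison for two secondary endpoints, and it should be corrected. Following Sections 10.2 and 10.3 as written gives overall percentages beside unnamed published ones, and a difference could come from severity mix with no device effect. The size of roughly 4 to 11 points for mRS 0-2 and 2 to 5 points for mortality depends wholly on the assumed stratum rates and mixes. A flatter gradient or a closer match between cohorts gives less. The risk is misinterpretation, not a wrong error rate.

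A reader might infer that NIHSS stratification would isolate the device effect. At n = 50, against external series, it cannot. It makes a shifted mix visible and removes part of its influence.

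**What to change.** Amend Sections 10.2 and 10.3 as follows:

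- Name the published comparator series before data review. The remaining steps depend on this.
- Report this study's pre-treatment NIHSS and pre-stroke mRS distributions beside the values that each series gives.
- Report mRS 0-2 and 90-day mortality with exact 95% intervals for all subjects, as the headline result, and in fixed NIHSS bands: <6, 6-15 and >15.
- Make each comparison in the subjects who fall within that series' NIHSS entry range.
- Where a series gives rates by NIHSS, set the observed count against the expected count, that is, the sum over bands of subjects in the band × published rate.
- State that all of this is descriptive, that band counts will be small, and that it reduces but does not remove case-mix confounding and does not correct selection arising from post-procedure consent.

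The cost is analysis-plan wording and a few extra tables. No new data, visits or eligibility changes are needed. The downsides are wide intervals within bands, and comparisons on fewer than 50 subjects wherever a series has a narrower NIHSS range.

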## 5 RISK / BENEFIT ANALYSIS

### 5.1 Potential Risks

The potential risks of mechanical aspiration thrombectomy for acute ischemic stroke treatment are well understood. Patients were informed of procedural risk and consent to the procedure per the Hospital's standard practice. This is an observational study with patient consent after a "standard of care", non-research mechanical thrombectomy procedure and hospitalization. There is no additional risk of a 3 month visit.

The potential risks of participation in this study are clearly identified in the subject informed consent form and are to be explained to the patient and/or their legal representative prior to participating in the study.

### 5.2 Potential Benefits

There is no guarantee or certainty that the subjects will benefit from this study. Data collected in this study may provide information for your doctor to treat future patients with a stroke.

### 5.3 Minimization of Foreseeable Risks

The Aspiration Catheter has been tested during the development process, including mechanical testing, *in vitro* testing, and animal testing. Standardized biomaterial safety testing has confirmed that the device is safe and comparable to legally marketed devices. Currently there is no Clinical Investigation data.

The sites participating in the study must agree to conduct the study in compliance with the protocol, GCP, and applicable local and international regulatory requirement(s).

## **6 STUDY POPULATION**

### **6.1 Study Population**

The observational study population is patients diagnosed with large vessel occlusion acute ischemic stroke within 8 hours of stroke onset treated with mechanical aspiration thrombectomy with the Q Aspiration Catheter as first line therapy. The Q Aspiration Catheter must be used according to the IFU to be included in the study. All study candidates (or legal representative) must be able to provide written informed consent and agree to be followed at 3 months post-procedure.

### **6.2 Number of Subjects**

Up to 50 subjects may be enrolled at up to 5 investigational sites in Spain. A center may enroll a maximum of twenty subjects.

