## **7.2 Subject Information and Consent**

Subjects must be informed about the study prior to enrollment. Only those subject's (or subject's legal representative) who voluntarily provide written consent will be allowed to participate in the study. The original signed consent form should be retained in the patient's study records and a copy should be provided to the patient or legal representative. If the patient is unable to provide informed consent or is deceased prior to consenting, a legally authorized representative may consent to use the patient's medical record.

A sample informed consent document suitable for use in this study will be provided. Iterations of this document must be approved by the reviewing Ethics Committee and the sponsor or sponsor-designate. Subjects must be presented with the most current EC approved version of the consent form for signature and study enrollment. The consent form and consent discussion should be in a language the subject understands. No study related data may be collected prior to patient consent. Study subject's must be consented prior to or at the study 3 month visit.

Subjects may withdraw participation at any time during the investigation without sacrificing their rights as a patient or compromising their quality of medical care.

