# **8 STUDY PROCEDURES**

## **8.1 Screening and Enrollment**

All patients diagnosed with acute ischemic stroke who undergo mechanical thrombectomy with the Q Aspiration Catheter as first line therapy, without regard to gender, are eligible for screening to participate in the clinical study. Patients will be screened based on the study inclusion and exclusion criteria after the procedure.

A screening log should be kept of all subjects in whom the Q Aspiration Catheter was used to prevent bias in subject selection. Death may be added to the screening log as reason for screen failure, if applicable.

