**TABLE 3 DATA COLLECTION**

Assessment	Baseline	Procedure	Post Procedure	Day 7 or Prior to Discharge	3 Month Follow-up
Visit Window	< 8 hours from stroke onset	< 8 hours from stroke onset	0 - 36 hours post procedure	1 day prior or day of discharge/transfer or Day 7	90 - 120 days post-procedure
Informed Consent			X 	X 	X 
Medical History	X				
Vitals	X				
Neuroimaging (CT/MRI)	X		X		
NIHSS	X		X		
mRS	X				X

Procedure and device use data		X			
Serious Adverse Event Collection		X	X	X	X

1 Informed Consent may happen at any time after the procedure but must happen prior to the initiation of the 3 month visit (but may be signed at the beginning of the visit)

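### Eligible patients need not be approached consecutively, and enrolment can follow knowledge of the outcome, so the analysed sample can be selected in the device's favour

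*Combined protocol and SAP*

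**What the plan says.** All references are to the combined protocol and SAP.

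- **Size (6.2).** "Up to 50 subjects may be enrolled at up to 5 investigational sites in Spain", and "A center may enroll a maximum of twenty subjects".
- **Inclusion (6.3).** "Subjects who meet the following criteria may be included in the study".
- **Screening (8.1).** "Patients will be screened based on the study inclusion and exclusion criteria after the procedure".
- **Consent (Table 3, footnote 1; also 7.2).** "Informed Consent may happen at any time after the procedure but must happen prior to the initiation of the 3 month visit". That visit falls at 90 to 120 days (8.5).
- **Safeguard (8.1).** "A screening log should be kept of all subjects in whom the Q Aspiration Catheter was used to prevent bias in subject selection".
- **Deaths (8.1).** "Death may be added to the screening log as reason for screen failure, if applicable".
- **Representative consent (7.2).** Where the patient is incapable of consenting or "deceased prior to consenting, a legally authorized representative may consent to use the patient's medical record".
- **Analysis (10.2).** The analysis set is the consented subjects. Endpoints are to be set against published outcomes, with no hypothesis test and no power calculation.

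**The concern.** In a single-arm study the comparison with published rates means something only if the enrolled patients represent those treated. Here the decision to offer a place can be taken after the angiogram, after the day-1 scan and NIHSS, and after a death in the following weeks. No section requires every eligible patient to be approached, or approached in any order.

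If patients who did badly are less likely to be approached or consented, final mTICI 2b-3 and mRS 0-2 read too high, and symptomatic haemorrhage, embolization to a new territory and mortality read too low. The independent core laboratory (11.7, 13.2) protects how an angiogram is graded but not whose angiogram is graded, since 8.3 sends films only after consent. Section 7.2 bars collection of study data before consent, so the plan would hold no outcome data on patients passed over and the bias could not be corrected afterwards. Section 4.1 aims to demonstrate safety and performance, and 5.3 says there are no clinical investigation data yet, so these rates would carry weight.

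**Working it through.** The plan has no derived figure to reproduce: 10.2 says that the sample size does not rest on power. The check has three steps.

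**1. What the site can know when it offers a place**

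- Operator's view of revascularization and of new-territory embolization: known at the end of the procedure (8.3), before screening.
- Day-1 imaging and NIHSS, hence haemorrhage status: 0 to 36 hours (8.4), which can precede consent.
- Death before the 3-month visit: can precede consent, and 8.1 foresees it.
- 90-day mRS: formally scored at the visit, after consent. Only an informal impression of recovery is available earlier.

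**2. What the limits do**

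- Places if all five sites reach their limit: 5 × 20 = 100, against 50 in total.
- Fewest sites that can supply 50: 50/20 = 2.5, so 3.
- Largest share from one site: 20/50 = 40%.

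The site limit stops one centre from dominating. It does not select on outcome, and the total of 50 may bind first.

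**3. How far selection could move a rate**

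Let b be the true rate of a bad outcome among eligible patients, and r the chance that a patient with that outcome is enrolled, relative to one without it. Then

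observed bad rate = b·r / (b·r + 1 − b).

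The documents give neither b nor r, so all values below are assumptions.

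- Revascularization failure, b = 0.15 (85% success):
  - r = 0.8: 0.12/0.97 = 12.4%, so success reads 87.6%.
  - r = 0.5: 0.075/0.925 = 8.1%, so success reads 91.9%.
  - r = 1.25: 0.1875/1.0375 = 18.1%, so success reads 81.9%.
- Mortality, b = 0.20:
  - r = 0.75: 0.15/0.95 = 15.8%.
  - r = 0.5: 0.10/0.90 = 11.1%.
  - r = 1.25: 0.25/1.05 = 23.8%.
  - With r = 0.5 and b from 0.10 to 0.25, the reading runs from 5.3% to 14.3%.
- Symptomatic haemorrhage, b = 0.05, r = 0.5: 0.025/0.975 = 2.6%.
- mRS above 2, b = 0.50, r = 0.5: 0.25/0.75 = 33.3%, so good outcome reads 66.7%.

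At r = 1 nothing changes.

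The outer bounds, assuming 60 eligible patients for 50 places, are:

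- 51 successes and 9 failures (85%): between (50 − 9)/50 = 82% and 50/50 = 100%.
- 12 deaths and 48 survivors (20%): between (50 − 48)/50 = 4% and 12/50 = 24%.

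If exactly 50 are eligible and all enrol, there is no selection.

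For scale, the exact 95% interval for 43 of 50 (86%) is 73.3% to 94.2%. A shift of about 7 points (91.9 − 85 = 6.9) would be lost within sampling error, so the results themselves would not reveal it.

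**The case against.** The best defence is that the sponsor saw the risk. Section 8.1 calls for a log of every patient treated with the device, expressly against selection bias, and 7.2 lets a representative consent for a patient who cannot consent or has died. The study is descriptive and tests nothing. The endpoint mTICI is the core laboratory's reading, so the site knows only the operator's impression.

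Part of this stands. The log and the representative route are real provisions, and a site that used both fully could enrol without bias. But the log is worded as a recommendation, obliges nobody to approach anyone, and appears nowhere in the analyses of 10.2 and 10.3. Representative consent is optional, and 8.1 lets the same death be logged as a screen failure. The operator's impression is enough to select on.

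Three stronger readings are tempting, and the documents do not support them.

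- **That the limit of 20 per site causes the bias.** The same risk exists without it. The limits matter only if they bind, because the order of consent then decides who gets a place.
- **That every endpoint is pushed upward, or that the direction is certain.** Favourable selection would raise the success measures and lower the harm measures, and the bounds above run both ways.
- **That patients needing a representative sign later and find places gone.** This is plausible, but Table 3 sets no different timing for representatives and the documents give no data on it.

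**Conclusion.** The concern holds as a weakness in design: the plan's own rules permit enrolment in the light of the outcome, and its one stated safeguard against selection records patients without controlling who is approached. The weakness bears on both primary endpoints and on the secondary endpoints, least directly on the 90-day mRS, which is scored after consent.

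The size is not determined by the documents. If bad outcomes are enrolled at half the rate of good ones, an assumed 85% success reads 91.9% and an assumed 20% mortality reads 11.1%; with equal enrolment there is no bias. These figures show what the plan leaves open, not what will happen. For mortality alone the text gives a documented route to understatement, through the unreconciled rules in 7.2 and 8.1. The change should be made, and no sample-size figure is affected.

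**What to change.** - **6.3.** Replace the permissive opening sentence with one under which patients meeting the criteria are to be included once consent is given.
- **8.1.** Add: from site activation, every patient who meets the clinical criteria of 6.3 and 6.4 (or the legal representative) is approached for consent in order of procedure date until enrolment closes. Any eligible patient not approached is recorded as a protocol deviation.
- **8.1 and 10.2.** Make the screening log mandatory and report from it the numbers treated, eligible, approached and consented, with reasons for non-enrolment, including death. A consecutive rule cannot remove refusals, and this report lets a reader judge how much they matter.
- **7.2 and 8.1.** Reconcile representative consent for a deceased patient with death as a screen failure, so that eligible deaths are not dropped by default.

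Cost: a few sentences and some site training. No extra patients or assessments are needed. The downside is that sites must approach patients and representatives who are harder to consent, with slightly more work on the log.
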